1. PREVIOUS STUDY HISTORY

Has this study ever been reviewed and rejected/disapproved by another IRB prior to submission to this IRB?

No Yes – if yes, please explain: | |

2. BRIEF SUMMARY OF RESEARCH

- *The summary should be written in language intelligible to a moderately educated, non-scientific layperson.*
- *It should contain a clear statement of the rationale and hypothesis of your study, a concise description of the methodology, with an emphasis on what will happen to the subjects, and a discussion of the results.*
- *This section should be ½ page*

Diabetes control is often assessed by tests of glucose levels over time, such as the glycosylated hemoglobin A1c (HbA1c) and fructosamine. In the later stages of chronic kidney disease (CKD) there is limited data available on the utility of these tests. There are reasons to believe that the tests may be less accurate in this population. Continuous glucose monitoring (CGM) offers an effective method for understanding the totality of glucose exposure and incidence of both hyperglycemic and hypoglycemic excursions. In the proposed study we plan to utilize CGM in patients with late stage CKD stages 3b-5 to 1) determine accuracy of HbA1c and serum fructosamine testing as measures of glucose control in patients with Type 2 Diabetes Mellitus (T2DM), 2) better understand test characteristics in the late stage CKD population (correlation, linear equation, slope, Y intercept, average glucose at different HbA1c levels), 3) develop a preliminary understanding of how test characteristics differ in late stage CKD compared to other patients with diabetes, 4) quantify time burden and number of episodes of hypoglycemia, 4) study hyperglycemic burden and 5) analyze glucose variability. The research staff will explain the study to patients that meet all inclusion criteria. Patients will get time to understand the study, review the consent document, ask questions to the PI, and then provide their consent to participate in the study. On Day 1 of the study, a CGM (Freestyle Libre) device will be placed on patients with CKD 3b-5 which will be worn for 14 consecutive days. Patients will return on Day 14 to remove the CGM device. HbA1c and fructosamine values will be drawn on Day 14 and these results will be compared with average glucose monitoring values as recorded on the CGM device. Incidence, duration, and severity of both hypoglycemic and hyperglycemic events will be analyzed. It is our hypothesis that there will be significant variability in the serum HbA1c values when compared with calculated HbA1c from CGM readings. We also hypothesize that the results will reflect a greater incidence of hypoglycemia in this population by CGM analysis.

3. INTRODUCTION/BACKGROUND MATERIAL/PRELIMINARY STUDIES AND SIGNIFICANCE

- *Describe and provide the results of previous work by yourself or others, including animal studies, laboratory studies, pilot studies, pre-clinical and/or clinical studies involving the compound or device to be studied.*
- *Include information as to why you are conducting the study and how the study differs from what has been previously researched, including what the knowledge gaps are.*
- *Describe the importance of the knowledge expected to result*

- Studies evaluating the accuracy of HbA1c and fructosamine values in patients with T2DM and CKD 3b-5 is scarce. A pilot study by Konya, Nq, Cox, et al., evaluated the accuracy of HbA1c in 15 T2DM patients with CKD3-4 receiving iron or erythropoiesis and concluded that other glycemic markers such as fructosamine or glycated albumin maybe valuable markers in assessing glycemic control in this patient population. Another pilot study by Vos, Schollum, et al., evaluated HbA1c, glycated albumin, and fructosamine in 25 patients with CKD 4-5 matched with T2DM patients with no renal dysfunction. These patients wore a CGM device for only 48 hours. The results of this study indicated that glycated albumin was a better marker than fructosamine and HbA1c in patients with CKD 4-5.
- This investigation is an attempt to add to the current available literature by assessing the accuracy of HbA1c and evaluating if fructosamine and/or CGM data are better tools for short term and long-term diabetes management in patients with CKD 3b-5 (not on hemodialysis (HD)) specifically. Our aim is also to assess the incidence of hypoglycemic and hyperglycemic excursion in these patients by CGM analysis.
- This study allows us to understand which marker (HbA1c, fructosamine, CGM data) is most reliable for diabetes management in patients with CKD 3b-5. Hypoglycemia in this specific subset of patients poses significant risks to increase morbidity and mortality. Improvement in such knowledge of glycemic control will lead to decreased morbidity and mortality in this population.

4. OBJECTIVE(S)/SPECIFIC AIMS AND HYPOTHESES

- *A concise statement of the goal(s) of the current study.*
- *The rationale for and specific objectives of the study.*
- *The goals and the hypothesis to be tested should be stated.*

- The goals of our study is to 1) determine accuracy of HbA1c and serum fructosamine testing as measures of glucose control, 2) better understand test characteristics in the late stage CKD population (correlation, linear equation, slope, Y intercept, average glucose at different HbA1c levels), 3) develop a preliminary understanding of how

test characteristics differ in late stage CKD compared to other patients with diabetes, 4) quantify time burden and number of episodes of hypoglycemia, 5) study hyperglycemic burden and 6) analyze glucose variability.

- It is our hypothesis that there will be significant variability in the serum HbA1c values when compared with calculated HbA1c from CGM readings. It is our hypothesis than the incidence of hypoglycemia will be high in patients with CKD 3b-5.

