10. ENDPOINTS

- *Describe the primary and secondary study endpoints*
- *Describe any primary or secondary safety endpoints*

- Primary End-Points: 1) Correlation between HbA1c and mean glucose concentration measured by CGM; 2) Characterization of hypoglycemic events, number, severity and duration. (Also, a safety end-point).
- Secondary End-Points: 1) Correlation between serum fructosamine and mean glucose concentration measured by CGM, 2) Determination of HbA1c and serum fructosamine regression equation, slope, Y intercept, average glucose at different test levels, 3) Number of hyperglycemic events and duration of each hyperglycemic event, 4) Study glucose variability as measured by mean amplitude of glucose excursion

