12. STATISTICAL ANALYSIS

- *Describe how your data will be used to test the hypotheses.*
- *State clearly what variables will be tested and what statistical tests will be used.*
- *Include sample size calculations.*
- *If this is a pilot study, state which variables will be examined for hypothesis generation in later studies.*

Patients with less than 7 days of CGM measurements will be excluded from analysis. Arithmetic mean glucose (AMG) will be calculated for each patient from

all CGM glucose measurements. A simple linear regression model will be applied to estimate the relationship between AMG and HbA1c. Once the relationship is established through the model, prediction of mean AMG together with 95% confidence intervals will be calculated at different levels of HbA1c. Influence of factors such as age, gender on the relationship between HbA1c and AMG will be examined through a multivariate regression model. Slopes and intercepts of the regression equations for the individual subgroups will be compared to those of the simple linear regression model. A quadratic regression model will also be applied if the relationship between the two variables is not linear. The same analysis will be performed to establish the relationship between AMG and serum fructosamine. Linear and quadratic regression models will be applied to estimate the relationship between AMG and HbA1c and serum fructosamine. If a linear relationship is established then slope, Y-intercept and correlation coefficient will be calculated. Mean AMG at different levels of HbA1c and serum fructosamine will be calculated. Glucose variability will be calculated as MAGE scores. First all the local maximum/minimum values are determined. The next step is an assessment of maximum/minimum pairs against the standard deviation (SD). If the difference from minimum to maximum is greater than the SD, this variation from mean measure is retained. If the local maximum/minimum is less than 1 SD it is excluded from further calculations. These troughs are retained and summed to achieve the MAGE score.

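### The first hypothesis compares measured HbA1c with CGM-calculated HbA1c, but no equation, paired difference or agreement analysis is planned for that comparison

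*Combined protocol and SAP*

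**What the plan says.** Section 4 gives the hypothesis: "It is our hypothesis that there will be significant variability in the serum HbA1c values when compared with calculated HbA1c from CGM readings". Section 2 repeats it. The first goal in Section 4 is to "determine accuracy of HbA1c and serum fructosamine testing as measures of glucose control".

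The summary in Section 2 says of the Day 14 blood results that "these results will be compared with average glucose monitoring values as recorded on the CGM device".

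Section 10 makes the first primary endpoint "Correlation between HbA1c and mean glucose concentration measured by CGM".

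Section 12 fits a simple linear (or, if needed, quadratic) regression with AMG as the predicted quantity. Its outputs are:

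- "If a linear relationship is established then slope, Y-intercept and correlation coefficient will be calculated";
- "prediction of mean AMG together with 95% confidence intervals will be calculated at different levels of HbA1c";
- for subgroups, "Slopes and intercepts of the regression equations for the individual subgroups will be compared to those of the simple linear regression model".

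The same analysis is planned for fructosamine.

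**The concern.** The quantity in the hypothesis is a departure: how far a patient's measured HbA1c lies from the value that the CGM trace implies. Computing it requires an equation that turns CGM glucose into HbA1c, a difference for each patient, and a summary of those differences. Sections 10 and 12 supply none of the three. They describe how strongly two quantities in different units move together and what line joins them. That answers the second goal (test characteristics). It answers the first goal and the hypothesis only in part.

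The study's premise is that HbA1c may be less accurate in late-stage CKD, and one form that inaccuracy can take is systematic bias. The first primary endpoint cannot register such bias. If the equation is chosen only after the data are seen, the size and even the sign of the mean difference can depend on that choice.

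**Working it through.** **Inputs.** Section 8 gives n = 80 and expects everyone to complete. Section 12 excludes patients with under 7 days of CGM, and Section 16 withdraws patients whose diabetes medication is changed. The documents give no r, SD, precision target or derivation of 80, so there is no planned figure on this point to reproduce. A case of 60 evaluable patients is shown as an assumption.

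**1. Trace the hypothesis through the plan.** The CGM-calculated HbA1c is named in the hypothesis sentences of Sections 2 and 4 and nowhere else. The comparison in Section 2 is with average glucose, and it names no method. The only benchmark that Section 12 gives for slopes and intercepts is the study's own overall line.

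**2. What r, slope and intercept do under bias.** Replace measured HbA1c, H, by a + bH with b > 0.

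- r with AMG is unchanged for any a and b.
- The slope of AMG on HbA1c is divided by b. HbA1c reading 20% low (b = 0.8) multiplies the slope by 1/0.8 = 1.25.
- A constant shortfall of 0.7 points leaves r and slope unchanged. It moves only the intercept and the predicted AMG.

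Slope and intercept therefore respond to bias, but a reader can see it only against a line from outside the study.

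One simulated sample of 80 illustrates this (assumed: calculated HbA1c mean 7.5, SD 1.2; error SD 0.6):

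| Measured HbA1c | r | Mean difference | 95% limits |
|---|---|---|---|
| no added bias | 0.872 | 0.03 | −1.16 to 1.21 |
| shifted by −1.0 | 0.872 | −0.97 | −2.16 to 0.21 |

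**3. Why the equation must be external.** A least-squares line passes through the two sample means. If calculated HbA1c came from this cohort's own line, fitted in either direction, the mean of measured minus calculated would be zero by construction.

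**4. Precision of an agreement analysis.** In units of the SD of the differences:

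- Mean difference, 95% CI half-width: t(n−1)/√n. For n = 80, 1.99/√80 = 0.22. For n = 60, 2.00/√60 = 0.26.
- Each limit of agreement: t(n−1)·√(1/n + 1.96²/(2(n−1))). For n = 80, 1.99·√(0.0125 + 0.0243) = 0.38. For n = 60, 2.00·√(0.0167 + 0.0326) = 0.44.

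**5. Interval for the mean against interval for a patient.** Let s be the residual SD and d the distance from mean HbA1c in SDs.

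- Planned CI of the mean: t(n−2)·s·√(1/n + d²/(n−1)).
- Individual prediction interval: t(n−2)·s·√(1 + 1/n + d²/(n−1)).

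At n = 80:

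| d | CI half-width | Prediction half-width | Ratio |
|---|---|---|---|
| 0 | 0.223 s | 2.003 s | 9.0 |
| 1 | 0.316 s | 2.016 s | 6.4 |
| 2 | 0.500 s | 2.053 s | 4.1 |

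At d = 0 the ratio is √(n+1): √81 = 9.0, or √61 = 7.8 with 60 evaluable.

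**The case against.** The strongest reply is that the planned outputs already carry the information. Under any linear conversion, calculated HbA1c is a linear transform of AMG, so its correlation with measured HbA1c is the primary-endpoint r. The fitted line, set against any external line, would give the average departure. This stands. A reader might infer that the plan can say nothing about departure; the documents do not support that. What is missing is the specification: no external line is named, and the paired comparison is not planned. A residual SD would also come out of the regression, but Section 12 does not list it, and it measures scatter of glucose about this cohort's own line.

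A second reply is that the interval for mean AMG is right for the second goal, which asks for average glucose at different HbA1c levels, and that Section 12 labels it correctly. This also stands. A reader might infer that the interval is an error; it is not. The ratio of 9.0 follows from simple regression at n = 80 and is not a defect of this plan. Prediction intervals are therefore a secondary addition.

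Third, limits of agreement would mix HbA1c error with CGM error, the 7-14 day window and the choice of equation, and they do not cover the fructosamine half of the first goal. That is a reason to state these limitations and keep the regression. It does not justify leaving the hypothesis without its own analysis.

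**Conclusion.** The point holds and should be fixed before analysis. Followed exactly, the plan does not produce the comparison that its first hypothesis states, and its first primary endpoint is insensitive to constant and proportional bias. The correlation and regression remain valid for the second goal.

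The tracing and the bias result need no numerical assumption. The precision factors at n = 80 assume that every recruited patient is evaluable. The 60-patient figures and the simulated sample are illustrations.

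Two further inferences go beyond the documents. A reader might assume that the data are already in hand. Section 9 gives only anticipated enrolment dates, and Section 22 says only that 24 subjects consented under the previous protocol; the measurements are planned, and no more than that can be said. A reader might also extend the point to the goal to "develop a preliminary understanding of how test characteristics differ in late stage CKD compared to other patients with diabetes". That goal is worded as preliminary and is a separate matter.

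**What to change.** Amend Section 12, using measurements already planned for collection:

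1. Before analysis, name one external equation for CGM-calculated HbA1c. Report measured minus calculated HbA1c as the mean difference with 95% CI, the SD of the differences, and 95% limits of agreement with CIs, with a difference plot. State that the limits also contain CGM error, the effect of the 7-14 day window and the choice of equation.
2. Secondary: report individual 95% prediction intervals for AMG beside the planned CI of the mean.
3. Keep the correlation and regression for the second goal and for fructosamine.

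No new patients or measurements are needed. The cost is a little more analysis, intervals that look wider, and a result that depends on the equation, which is why it must be fixed in advance.

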5. RESOURCES AVAILABLE TO CONDUCT THE HUMAN RESEARCH

- *Explain the feasibility of meeting recruitment goals of this project and demonstrate a potential for recruiting the required number of suitable subjects within the agreed recruitment period*
 - *How many potential subjects do you have access to?*
- *Describe your process to ensure that all persons assisting with the trial are adequately informed about the protocol and their trial related duties and functions*

- We have access to an estimated 300 patients with CKD 2-5 and ESRD on HD at the Northwell Division of Nephrology and Endocrinology and at Winthrop University Hospital's Division of Nephrology clinical practice. Among these patients, we hope to identify T2DM patients with CKD 3b-5 not on HD and aim to recruit 80 subjects for our study.
- The Division of Nephrology and Endocrinology at Northwell and The Division of Nephrology at Winthrop Hospital will have an initial meeting with all research staff to explain the study protocol and design. Moving forward, the PI and assistant investigators will frequently meet with the research staff at scheduled meetings to discuss updates and concerns relating to the study..

6. RECRUITMENT METHODS

- *Describe the source of potential subjects*
- *Describe the methods that will be used to identify potential subjects*
- *Describe any materials that will be used to recruit subjects. A copy of any advertisements (flyers, radio scripts, etc.) should be submitted along with the protocol.*
- *If monetary compensation is to be offered, this should be indicated in the protocol*

- Patients will be recruited from the offices of Northwell Division of Nephrology and Endocrinology and at Winthrop University Hospital's Division of Nephrology clinical practice.
- Among these patients, we hope to identify T2DM patients with CKD 3b-5 not on HD and aim to recruit 80 subjects for our study. Patients will be identified for eligibility by their treating physicians or by prescreening by study personnel of office practice patients.

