7. ELIGIBILITY CRITERIA

- *Describe the characteristics of the subject population, including their anticipated number, age, ranges, sex, ethnic background, and health status. Identify the criteria for inclusion or exclusion of any subpopulation.*
- *Explain the rationale for the involvement of special classes of subjects, such as fetuses, pregnant women, children, prisoners or other institutionalized individuals, or others who are likely to be vulnerable. You cannot include these populations in your research, unless you indicate such in the protocol*
- *Similarly, detail exclusionary criteria: age limits, special populations (minors, pregnant women, decisionally impaired), use of concomitant medications, subjects with other diseases, severity of illness, etc.*

- We anticipate recruiting 80 subjects for this study. We anticipate a fair distribution of males and females, Caucasians, African Americans, and people from other ethnic groups. We anticipate that most patients in this age group are relatively healthy with possibly 1-5 past medical health problems.
- Inclusion Criteria: patients who are 18 years and older with the ability to speak and understand English and with T2DM AND CKD stages 3b-5. Vulnerable populations would include elderly and minorities, as listed in section 26 below for vulnerable populations. There are minimal risks of participating in this study for all subjects including vulnerable populations.
- Exclusion criteria: patients with Type I DM, ESRD on HD, hemoglobinopathies, who have received red blood cell transfusions in the last 12 weeks, with hemoglobin <9, current use of acetaminophen on a daily basis, steroid treatment in the prior 12 weeks, greater than 50% change in diabetes medications or new diabetes medications started in the prior 12 weeks, patients who are currently pregnant.

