19. POTENTIAL BENEFIT TO SUBJECTS

- *Explain what benefits might be derived from participation in the study, noting in particular the benefit over standard treatment (e.g. a once-a-day administration instead of four times a day, an oral formulation over an IV administration).*
- *Also state if there are no known benefits to subjects, but detail the value of knowledge to be gained*

The CGM data analysis can be provided to subject's endocrinologist if requested by the subject at the end of their participation. The subject's endocrinologist may make medication or insulin adjustments based on the CGM data which may be beneficial to the patient.

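### Patients enter through physician discretion or prescreening with no consecutive approach and no record of route, so selection could shift both primary end-points undetected, in a direction the documents do not fix.

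*Combined protocol and SAP*

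**What the plan says.** Section 6 (Recruitment Methods) gives two ways in, joined by an *or*: "Patients will be identified for eligibility by their treating physicians or by prescreening by study personnel of office practice patients". It states no order of approach and no expected share per route. Section 7 gives the target ("We anticipate recruiting 80 subjects for this study"), and Section 5 the source: "We have access to an estimated 300 patients with CKD 2-5 and ESRD on HD".

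The primary end-points in Section 10 are "Correlation between HbA1c and mean glucose concentration measured by CGM" and "Characterization of hypoglycemic events, number, severity and duration". The hypotheses in Section 4 concern levels in this one group. The first reads "It is our hypothesis that there will be significant variability in the serum HbA1c values when compared with calculated HbA1c from CGM readings"; the second is that "the incidence of hypoglycemia will be high in patients with CKD 3b-5".

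Section 19 allows the CGM analysis to go to the subject's endocrinologist if the subject asks, and adds: "The subject's endocrinologist may make medication or insulin adjustments based on the CGM data which may be beneficial to the patient".

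Section 12 (Statistical Analysis) names age and gender as examples of factors to examine. It does not mention route or site. Section 8 gives 80 expected recruits and no count of patients to be prescreened or invited.

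**The concern.** With no control group, how patients come into the sample is the main protection against bias in both primary end-points. One of the two routes is discretionary. Section 19 gives a plausible reason for using that discretion: a CGM report is most useful for a patient whose lows are suspected or whose HbA1c does not fit other readings, and those are the features the study expects to find. A physician might equally put forward stable, cooperative patients.

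In either case the sample could differ from the eligible CKD 3b-5 population, and the plan collects nothing that would show it. The comparison with other patients with diabetes (goal 3 in Section 4) would inherit the problem, because a selection effect could not be told apart from an effect of CKD. A larger sample under the same recruitment rule would not remove it.

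**Working it through.** The plan gives no figure to reproduce: 80 comes without a precision target or power calculation. What follows is an illustration.

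**From the documents.** n = 80 (Section 7). The accessible pool is about 300 (Section 5), but it includes CKD 2-3a and hemodialysis patients and is not limited to T2DM. The eligible number M is therefore below 300 and is not stated.

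**Assumed.** True proportion with any CGM hypoglycemia p = 30% (20% and 40% as a range); odds w = 2 or 3 that an affected patient is referred; M = 100, 150 or 200; half or all of the sample referred. The proportion affected stands in for end-point 2, which the protocol defines by number, severity and duration of events.

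**1. Sampling error.** SE = √(0.30 × 0.70 / 80) = 0.051. The 95% half-width is 1.96 × 0.051 = 0.100.

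**2. Hypoglycemia, drawn without replacement.** Let K = pM be the number affected. If m patients are referred, the expected number affected, μ, is the Wallenius noncentral hypergeometric mean, closely approximated by solving (1 − μ/K)^(1/w) = 1 − (m − μ)/(M − K).

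- All referred, M = 100, w = 2: μ ≈ 28.0. Check: (1 − 28/30)^(1/2) = 0.258 and 1 − 52/70 = 0.257. Observed 28.0/80 = 35%.
- All referred, M = 200, w = 3: μ ≈ 38.9; 38.9/80 = 49%.
- Half referred (40 first, then 40 at random from the rest), M = 100, w = 2: 16.7 + 40 × (30 − 16.7)/60 = 25.6; 25.6/80 = 32%.
- Half referred, M = 200, w = 3: 21.2 + 40 × (60 − 21.2)/160 = 30.9; 30.9/80 = 39%.

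| True 30% | Half referred, w = 2 / 3 | All referred, w = 2 / 3 |
|---|---|---|
| M = 100 | 32% / 33% | 35% / 37% |
| M = 150 | 34% / 37% | 40% / 45% |
| M = 200 | 35% / 39% | 42% / 49% |

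The shift is about 2 to 9 points with half referred (0.4 to 1.7 SE) and 5 to 19 points with all referred (1.0 to 3.6 SE). By the same method over the same M and w, a true 20% becomes 22-27% (half) or 24-35% (all), and a true 40% becomes 42-49% or 46-60%.

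**3. Arithmetic limits, either direction.** The maximum is min(1, pM/80) and the minimum is max(0, [80 − (1 − p)M]/80). At p = 30% the observed proportion can lie between 12.5% and 37.5% for M = 100, 0 and 56% for M = 150, and 0 and 75% for M = 200. A smaller eligible pool leaves less room for selection.

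**4. Correlation.** Assume bivariate normal HbA1c and mean glucose, with the third of patients having the largest absolute residuals w times as likely to enter, all patients selected this way, and an unlimited pool (so these are upper readings of the effect). In simulation the residual SD rises by a factor k = 1.167 (w = 2) or 1.257 (w = 3). The observed correlation is then r / √(r² + (1 − r²)k²). For r = 0.7:

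- w = 2: 0.7 / √(0.49 + 0.51 × 1.362) = 0.64
- w = 3: 0.7 / √(0.49 + 0.51 × 1.580) = 0.62

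For r = 0.5 the results are 0.44 and 0.42; for r = 0.8, 0.75 and 0.73. The Fisher 95% interval for r = 0.7 at n = 80 is 0.57 to 0.80, so a shift of this size lies inside ordinary sampling error.

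**The case against.** The other side has good points, and several limit the claim.

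- **Direction.** A reader might infer that referral must inflate both hypothesized results. The documents do not support that. Section 7 expects mostly relatively healthy patients, so selection could run the other way, and referral that only widens the HbA1c range could raise the correlation. Section 7 also excludes hemoglobinopathy, transfusion within 12 weeks, hemoglobin below 9, and new or substantially changed diabetes medication within 12 weeks. Section 16 withdraws subjects whose diabetes medication is changed during monitoring. These rules remove some causes of a doubtful HbA1c and some patients whose suspected lows have already been acted on. They do not address unexplained discordance or suspected lows that have not yet led to a change.
- **Size.** A reader might use the unlimited-pool formula pw/(pw + 1 − p), which gives 0.6/1.3 = 46% and 0.9/1.6 = 56% with all referred, and 38% and 43% with half. Section 5 rules out an unlimited pool. At M = 100, 56% is impossible, because the maximum is 30/80 = 37.5%.
- **Motive.** CGM data are released only at the subject's request, after participation, and to the endocrinologist. Two of the three recruiting practices named in Section 8 are nephrology. The incentive is plausible, not documented, and the prescreening route could be run across the whole practice.
- **Generality.** Convenience sampling is common in minimal-risk, single-group studies, and neither hypothesis has a numerical threshold that bias could push it across. That lowers the stakes. It does not supply the missing order of approach or record of route.

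**Conclusion.** The point holds as a gap in design and record-keeping. Section 6 permits discretionary entry, no section sets an order of approach or records the route, and both primary end-points depend on who enters. The plan could neither prevent nor detect selection, whichever way it ran.

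Its size is conditional. At an assumed true 30%, odds of 2 to 3 and 100 to 200 eligible patients, the observed proportion would be about 32-39% with half referred and 35-49% with all referred, against an SE of about 5 points. The effect therefore runs from negligible to larger than the 95% half-width of 10 points. The effect on the correlation is modest under the assumptions tried. The documents give none of p, w, M or the referred share, and they do not show that selective referral takes place. The change is worth making because it is cheap; no change in sample size follows.

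**What to change.** For remaining enrolment:

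1. Have study personnel prescreen the practice lists and invite every eligible patient in list or visit order, with treating physicians only confirming that contact is acceptable. Visit order fits more easily with Section 20, which says patients receive no mail or phone messages.
2. Keep a screening log with counts of eligible, invited and consented patients.
3. Record the recruitment route for every subject. For those already enrolled (Section 22 mentions 24 who consented under the previous protocol), record it as far as it can be established, since a single route cannot be applied to them in retrospect.
4. Add to Section 12 a sensitivity analysis that reports both primary end-points by route.

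Compare enrolled with non-enrolled patients only in aggregate and only if the IRB permits it. Section 25 seeks no HIPAA waiver, and an individual-level table of people who have not consented may need one.

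The cost is some prescreening time for existing staff, an IRB amendment, and less convenience for referring physicians. No extra subjects or study procedures are needed.
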